Secondary outcomes

- Proportion of participants without Ct detected on faces immediately following face wiping with the SuperTowel
- Proportion of participants without ocular or dry nasal discharge on faces immediately following washing/wiping protocol
- Mean log₁₀ reduction in load of Ct on faces immediately following the washing/wiping protocol
- Proportion of participants without *Ct* / ocular and nasal discharge on faces at 1, 2, 4, 6 and 8 hours following the washing/wiping protocol
- Mean log₁₀ increase in load of Ct on faces at 1, 2, 4, 6 and 8 hours following protocol
- Mean viable load of Ct found on the SuperTowel® samples after use.

The screening of such a large number of children offers an opportunity to conduct related analyses alongside our trial work. Some planned ancillary objectives are mentioned below.

- We will also compare the ability of a novel, quantitative metric vs current metrics (i.e. signs of ocular and nasal discharge), to predict recent personal cleaning practices, across the three methods.
- We will look for evidence of *Ct* in the stools of children with ocular infection, evidenced by PCR.
- We will evaluate the diagnostic ability of the rapid test used to screen for ocular infection as compared to ocular infection detected through PCR.

Methods

Study design

This is a three-arm, open, parallel-group randomised controlled trial.

Study setting and population

The study will be carried out in one *zone* in Oromia in districts with high TF prevalence in 1-9 year olds (TF1-9>40%) selected according to GTMP (Global Trachoma Mapping Project) data. We will confirm the *de facto* TF prevalence in 1-7 year olds (the eligible population for the study, see below) and the absence of recent - within the last 6 months; ideally as close to a year ago as possible -azithromycin mass drug administration (MDA) in selected *woredas* prior to commencing the study. The total population of the zone is estimated at 3.9 million . In some of the districts of this zone, trachoma surveillance survey (TSS) conducted in 2022, after five rounds of MDA, showed the TF prevalence is greater than 11% in children ages 1-9 years.

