- 8. Wipe the skin of the child's forehead using a moist, sterile gauze pad. Use a standardized, 11-point brown colour scale to score the colour of the darkest point within the darkest half-square inch (i.e., thumb-nail sized area) of each gauze pad. After scoring, photograph each wipe along with the colour scale and negative control (i.e., unused wipe).
- 9. Swab the child's face (under eye, across the cheek, and under the nostril) and both hands (fingers, palms and backs of both hands) according to a standardised swabbing protocol (Appendix 3). Swab caregivers' hands too as they will be washing the child's face. Record data
- 10. Round 1: For Protocols A-C: Instruct caregivers to wash the child's face with water only (Protocol A), with water and soap (Protocol B), or to wipe the child's face with the *SuperTowel* (Protocol C) following a standardised protocol according to intervention allocation. Ask a household member to bring water for face washing in the vessel they would normally use. The face should be washed using two hands and should last about 30 seconds. All parts of the face should be washed carefully, including around the eyes and nose. Provide ordinary non-medicated soap for Protocol B. The face and hands should not be dried and should not touch anything until the next swab is taken.
- 11. Wait 5 minutes for child's hands and face (and the caregivers' hands) to air dry if Protocols A or B have been followed, photograph the face and record whether the wash removed existing ocular and nasal discharge
 - 12. Immediately repeat swabbing of the child's face and hands and caregivers' hands Record.
 - 13. Request that the child's face is not washed or wiped again until the end of the study if possible, unless the child is particularly uncomfortable.
 - 14. Ask the caregiver to wash their hands with soap and swab hands again.
- 15. Swab child's face and hands of children and carers 1, 2, 4, 6 and 8 hours after face washing. At each time point photograph and record facial cleanliness (presence of ocular and nasal discharge, and flies) and record reported face or handwashing since the last swab was taken.

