The SuperTowel® is a product developed by RealRelief. It has been designed as a soap alternative product for emergency situations but also has potential for use in other water-scarce areas. The SuperTowel® is a durable fabric with a permanent anti-microbial bonding. The treated fabric must be dipped in water and then rubbed against the skin so that pathogens will be transferred to the fabric where they will be killed. Several laboratory test have demonstrated the bactericidal effect of the fabric against different bacteria (Appendix 4). The anti-microbial technology is achieved by long chains of carbon atoms attached to positively charged nitrogen atoms bonded to a silica layer on to the fabric. Each of these three elements have a specific function. The silica-based group functions as the antimicrobials anchor. The silica group is anchored through covalent bonds which are formed through standard hydrolysis reactions that allows the antimicrobial to be bond to almost any surface while allowing cross linking and polymerisation with other molecules. The positively charged nitrogen atom attracts negatively charged microbes including bacteria and fungi. The long chains of carbon atoms function as a needle that pierces the cell membrane of a microbe while it gets attracted towards to positively charged nitrogen atom causing membrane disruption. This membrane disruption results in leakage of cytoplasmic materials killing the microbe. When the negatively charged microbe gets drawn further on to the carbon atom chains it will eventually come in contact with the positive nitrogen atoms. This contact causes the electric balance to be disturbed and can cause the microbe to explode under its own osmotic pressure. The technology can offer complete protection against most pathogens, thereby giving a clean and microbe free hand. If the water is contaminated (e.g. grey water), the technology could remove the pathogens in the water absorbed by the towel. As the bonding is permanent the fabric does not call for replacement until it is damaged or lost. The SuperTowel® will reduce the amount of water needed for hand and face washing, reduce drainage problems that are often seen around hand washing facilities, and negate the need for soap.

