Analyses will be 'per-protocol' so efficacy can be assessed, but will be restricted to children with *Ct* on their face at baseline as determined by PCR. Participants will be analysed according to the protocol they performed. Primary comparisons will be between Protocols A and B and will compare the proportion of participants without *Ct* detected on faces immediately following face washing according to each protocol. In secondary analysis we will look at *Ct* removal following Protocol C, removal of oculo-nasal discharge following Protocols A-C and mean log₁₀ reduction in load of *Ct* on faces immediately following each Protocol. A further secondary analysis will compare how quickly the load of Ct builds up on the faces of infected children, following removal by each of these four methods. Regression analyses will be performed to evaluate the relative efficacy of the various cleaning methods for removing Ct from faces using 'washing with water' as the comparison. Another secondary analysis will assess the viable load of Ct found on the SuperTowel® samples after use, to give an indication of their potential role as fomites in transmission.

We will also compare the ability of a novel, quantitative metric vs current metrics (i.e. signs of ocular and nasal discharge), to predict recent personal cleaning practices, across the four methods.

We will look for presence of Ct in stool as determined by PCR.

As ocular infection is assessed through both rapid test and PCR, we also have the opportunity to compare the results to evaluate the diagnostic ability of the rapid test.

Data management

Data from the study will be jointly managed by the LSHTM and FHF team in Ethiopia, coordinated by the Ethiopian Project Manager and the PI. Data will be entered at the time of collection via electronic data capture on password protected Android Devices using the Open Data Kit (ODK) secure data capture system provided by LSHTM http://opendatakit.lshtm.ac.uk/. All data is automatically encrypted on the Android devices when the ODK form on the Android devices is filled and finalised. The ODK Collect app uses the public encryption key along with an encryption algorithm to convert the data in to an encoded (encrypted) form. Once the form is finalised, the data cannot be reopened or

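### The first post-cleaning assessment follows a 5-minute wait in the water and soap arms but no stated wait in the SuperTowel arm, so the immediate SuperTowel contrasts mix cleaning method with measurement timing

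*Protocol*

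**What the plan says.** Step 11 of the Procedure section sets a 5-minute wait for the child's face and hands and the caregiver's hands "to air dry if Protocols A or B have been followed". The same step then has the face photographed and the removal of discharge recorded. Step 12 follows with "Immediately repeat swabbing of the child's face and hands and caregivers' hands". Nothing in the Procedure gives a wait, of any length, for Protocol C.

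Three other places bear on this:

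- Step 10, which covers all three protocols, says "The face and hands should not be dried and should not touch anything until the next swab is taken". It is not limited to the washing arms.
- The section About the SuperTowel says "The treated fabric must be dipped in water and then rubbed against the skin", so the cloth is used wet.
- The Secondary outcomes include "Proportion of participants without Ct detected on faces immediately following face wiping with the SuperTowel", discharge status at the same moment, and the mean log10 "reduction in load of Ct on faces immediately following the washing/wiping protocol". The first secondary objective compares the SuperTowel with both washing arms.

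The Statistical Analysis section says "Primary comparisons will be between Protocols A and B".

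**The concern.** When arms are compared on an outcome read immediately after the intervention, the reading should be taken at the same interval in each arm. Here the interval depends on allocation: about 5 minutes in A and B, and none stated in C. Randomisation does not protect against this, because the difference arises after allocation. Adjustment cannot remove it either, because the wait is fully determined by the arm.

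Two things could differ for reasons other than how well each method cleans. One is the time available for ocular or nasal discharge to reach the face again. The other is the state of the skin when it is swabbed. The protocol treats early return as an open question: its Rationale names the Ct load of quickly returning discharge as something not yet studied. At stake is the interpretation of a named secondary objective, not the main result.

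**Working it through.** The point rests on procedure wording. The protocol gives no figure for it, so there is none to reproduce.

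**Step 1. Interval from end of cleaning to first assessment, by arm (Procedure, steps 10–12).**

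| Arm | Stated wait | First photograph, discharge record and swab |
|---|---|---|
| A, water | 5 minutes | about 5 minutes after cleaning |
| B, water and soap | 5 minutes | about 5 minutes after cleaning |
| C, SuperTowel | none stated | directly after wiping |

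**Step 2. Which outcomes use that reading.**

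- Affected, for C against A and C against B: immediate Ct detection, immediate log10 load reduction, immediate discharge removal.
- Affected conditionally: the increase in load at 1–8 hours, if the immediate swab is its starting value. The protocol does not say which value is used.
- Not affected: A against B, since both have the wait.
- Not affected: absolute Ct and discharge status at 1, 2, 4, 6 and 8 hours. Step 15 times these from face washing and the outcome list times them from the washing or wiping, not from the first swab.
- Not affected: viable load on the used towel, which is a one-arm outcome.

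**Step 3. How large a timing effect would have to be to matter.** The documents hold no data on recontamination within 5 minutes or on swab recovery from damp against dry skin. The calculation below is therefore an illustration under assumed shifts, not an estimate.

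Inputs: n = 47 children with facial Ct per arm and base detection b of 60% or 90% (the planning values in Sample size); two-sided level 0.05/3 = 1.7% (same section), for which the normal critical value is c = 2.394. The section prints 2.573 beside that level; this is a separate matter. Assume no true difference between arms, and that timing alone lowers detection in one arm by d, so q = b − d.

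Formulas, with m = (b + q)/2:

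- SE0 = √[2m(1 − m)/n]
- SE1 = √[(b(1 − b) + q(1 − q))/n]
- P(false difference) = 1 − Φ[(c·SE0 − d)/SE1] + Φ[(−c·SE0 − d)/SE1]

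Worked case, b = 0.90 and d = 0.05: m = 0.875; SE0 = √(0.21875/47) = 0.0682; SE1 = √(0.2175/47) = 0.0680; c·SE0 = 0.1633. The upper term is 1 − Φ(1.666) = 0.0479 and the lower is Φ(−3.136) = 0.0009, so P = 0.049.

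| Assumed shift d | Base 60% | Base 90% |
|---|---|---|
| 2 points | 1.9% | 2.2% |
| 5 points | 3.0% | 4.9% |
| 10 points | 7.7% | 14.8% |
| 15 points | 17.2% | 31.2% |

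A shift of a couple of points would hardly show. A shift of 10 points or more would distort the immediate SuperTowel contrasts materially. The documents do not say where in this range the truth lies.

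**The case against.** The best defence is that the wait exists to dry the skin. Washing by hand with water leaves a wet face that may not be dried, whereas a microfibre cloth described as saving water may leave little moisture. On that view the conditional wait brings the skin to a similar state before swabbing in every arm. This is plausible, but the protocol does not say it. The cloth is dipped in water, the bar on drying covers all arms, and a dry face in C would still be measured at a different interval from A and B.

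The defence also has points that stand. The SuperTowel objectives are secondary and are to be reviewed after an in vitro pilot. A second pilot is meant to refine data collection procedures, and the drying time could be settled there. The swabbing procedure in Appendix 3 is not available here and may say more.

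Four stronger readings are tempting, and the documents do not support them:

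- A reader might infer that every SuperTowel comparison is biased. The 1–8 hour status is already timed from cleaning in all arms, and the towel load has no comparator.
- A reader might infer that zero wait favours the SuperTowel. That follows only if the face is re-seeded within minutes. The Rationale raises quick return as a gap and gives no timescale; the timed data in the Introduction are at two and four hours. Swabbing damp skin could raise or lower recovery, so the net direction is unknown.
- A reader might take it as fact that the face in arm C is damp when swabbed. Residual moisture after wiping is not described.
- A reader might set an assumed shift against the planned 30-point difference (90% minus 60%). That difference belongs to water against soap, which is untouched; no planned difference is given for C.

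**Conclusion.** The point holds within a limited scope. As written, the interval between cleaning and the first assessment differs by arm, no reason is given, and analysis cannot separate that interval from the cleaning method. This affects the immediate contrasts of C with A and with B on Ct detection, log10 load reduction and discharge removal, and on build-up if the immediate swab is its starting value.

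Bias is possible but not demonstrated, and its size and direction are unknown. The percentages in the illustration depend wholly on the assumed shifts. The reading also assumes that field staff follow step 11 literally and that the appendix procedure does not impose a common wait. With the primary comparison intact, this is a cheap improvement to secondary outcomes and not a threat to the trial's main conclusion.

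**What to change.** In step 11, delete the condition that follows the words on air drying, so that the same 5 minutes runs from the end of cleaning to the photograph, discharge record and swab in all three arms. Record the actual times of end of cleaning, photograph and swab in the data form. The 1–8 hour clock needs no change. If the sponsor has a reason for keeping different intervals, the protocol should state it and still require the times to be recorded.

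The cost is one line of procedure, time fields in the form, and five more minutes per child in one arm of an 8-hour visit. With 470 enrolled in three equal arms, that is about 157 children × 5 minutes ≈ 785 minutes, or roughly 13 hours over the whole of fieldwork. It has to be done before swabbing starts, since a reading taken at the wrong interval cannot be recovered afterwards.

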King et al. [20] argue that a 'dirty face' is not a good predictor of whether a face has been washed. They conducted a randomised trial of 424 children to receive a standardised face wash or none, and observed faces for ocular and nasal discharge, dust, food and flies at three time points through the day and at baseline. A significant difference was observed in the presence of ocular discharge (P < 0.001) and dry nasal discharge (P < 0.001) between the washed and unwashed groups, but two hours after washing, the presence of ocular discharge predicted face washing in only 63% of children, reducing to only 54% in four hours from washing.

In our own studies conducted in Phase 1 of Stronger SAFE (Ethics reference: 14325), we asked 34 children aged 1-9 with TF/TI to wash their faces with either water only or water and soap. Each child was given instructions about washing their face properly and was observed to follow these instructions. We found that washing with soap and water was more effective at removing ocular discharge than washing with water only (89% vs 27%, p = 0.003). In comparison, nasal discharge was not effectively removed by any method: discharge was removed from 27% of 11 children with nasal discharge at baseline by washing with soap, and 50% of 14 children by washing with water (p=0.250 for comparison with washing with soap). However, only two of these children enrolled (both randomly assigned to wash with water only) were positive for Ct by ocular swab, so we were unable to fully test our hypotheses that face washing would reduce Ct load on the face — the relevant agent for transmission of infection.

Facial hygiene measures and metrics

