- 4. We need new metrics of facial hygiene that are valid, reliable and useful.

Study Aim and Objectives

The primary aim is to find the optimal facial hygiene practice to reduce the likelihood of *Ct* being present on the faces of infected children in order to improve the design of interventions for trachoma control. We hypothesise face washing with soap will reduce the amount of *Ct* found on infected children's faces

Our primary objective is to assess the relative effectiveness of face washing with soap and water compared with face washing with water only on the removal of *Ct* from the faces of children with ocular trachoma infection.

Our secondary objectives are to:

- Assess the relative effectiveness of face wiping (with a product called the 'SuperTowel'®) compared with face washing with water and face washing with water and soap on removal of *Ct* from the faces of children with ocular trachoma infection.
- Assess the relative effectiveness of three facial cleanliness methods on removal of ocular and nasal discharge on the faces of children with ocular *Ct* infection
- Assess the relative effectiveness of three facial cleanliness methods on the mean reduction in *Ct* load on the faces of children with ocular trachoma infection
- Assess how long it takes for Ct to return to children's faces following face washing or wiping.
- Assess the effectiveness of the product called the 'SuperTowel'® to kill (reduce viability) of Ct transferred to it

Objectives related to the 'SuperTowel'® will be reviewed following an *in vitro* pilot to confirm the properties of the 'SuperTowel'® in relation to killing *Ct* bacteria on contact.

A further aim is to evaluate the ability of a novel, quantitative metric to predict recent personal cleaning practices. The purpose of this study is to determine whether there are meaningful differences in the sensitivities of this novel metric vs current metrics (i.e. signs of ocular and nasal discharge) to detect differences in pre- and post-cleaning facial cleanliness, across different face cleaning practices.

We are also interested in learning whether spread of *Ct* through the gastrointestinal tract might be possible.

Outcome measures

Primary outcome

• Proportion of participants without *Ct* detected on faces immediately following face washing with soap and water, compared with the face washing with water only group (i.e. To assess whether soap is needed to remove *Ct* from faces or whether water alone is sufficient).

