The SuperTowel® has been developed to be an alternative to soap and water in situations where soap and water are scarce. It is a microfibre cloth that has been treated so that it kills pathogens that it absorbs. The treatment is permanently bonded to the cloth, so it cannot come off onto skin, or be washed off. SuperTowel® has been shown to be effective as a tool for hand hygiene in water-scarce regions (21-23), but its use for face washing will be a novel application.

An overview of the trial design showing screening and intervention allocation in Rounds 1 and 2 is shown in Figure 1.

[figure not shown]

Figure 1. Overview of Trial design.

Pilot study

We will carry out two small pilot studies as follows:

- 1. *In vitro* lab study to assess the ability of the *SuperTowel®* to kill *Ct* on contact.
- 2. Pilot study to test and refine trial screening and data collection procedures. To help set a cutoff time to ensure that included children still have infection (indicated by Ct on their faces)
 from the time of screening until the completion of all protocols, we will also follow up to 20
 ocular positive children included in the pilot for 7-10 days. Each day we will swab their faces
 (only) to test for Ct presence.

Procedure

On a rolling basis after screening, in households with eligible children recruited into the study:

- 1. Inform the female primary caregiver of children aged 1-7 years about the WASH sub studies and consent. Agree a convenient time to return to conduct the study. Request that the child's face is not cleaned or washed in the morning before your visit unless the child is particularly uncomfortable.
- 2. Set up examination station, and ask other HH members to stay at least 5 meters away from this
- 3. Use ODK form to capture all data (see Appendix 2 for indication of the contents of ODK form)
- 4. Examine children's eyes and assign a WHO grade and FPC grade to each conjunctiva

- 5. Take a conjunctival swab from the participant, according to a standardised swabbing protocol (Appendix 3). This swab will be used to confirm ocular *Ct* infection by polymerase chain reaction (PCR).
- 6. Take an air swab following standardised protocol.
- 7. Photograph and record current facial cleanliness, per qualitative cleanliness metrics (presence of ocular and nasal discharge, and flies) and any reported face and handwashing that has taken place that morning

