 - 16. Wipe the skin of the child's forehead using a moist, sterile gauze pad. Use a standardized, 11-point brown colour scale to score the colour of the darkest point within the darkest half-square inch (i.e., thumb-nail sized area) of each gauze pad. After scoring, photograph each wipe along with the colour scale and negative control (i.e., unused wipe).
 - 17. Ask the child to wash their face with soap and water to complete the study. Provide Soap for this purpose.
 - 18. Complete a brief risk factor survey.
 - Before leaving, thank the female primary caregiver and child(ren) and answer any outstanding questions
- 20. Collect stool sample from child.
- 21. Treat children for trachoma at end of the study.
- 22. Due consideration will also be given to the current COVID-19 pandemic by adhering to the national Standard Operating Procedures (SOP).

NB: We might also ask participants to allow us to video the face washing procedure and/or our team members completing the wipes and swabs. The purpose of these videos is for internal fidelity checks, and also to get a sense of the way that people typically wash faces in this setting.

Sample storage and management

All swab samples will be stored in $500\mu L$ 2SP transport medium and stored on ice packs in the field. Stool samples will be stored on ice.

All used SuperTowel® samples will be sealed in a biohazard bag (or in a 2SP transport medium inside 50ml falcon tubes, if feasible) immediately after use, and will not be reused on other participants.

About the SuperTowel®

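### No forehead wipe is scheduled straight after washing, so the new cleanliness metric cannot show immediate pre- to post-cleaning change against discharge

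*Protocol*

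**What the plan says.** Study Aim and Objectives sets a further aim: to find out whether the novel colour-scale metric and the current signs (ocular and nasal discharge) differ in their sensitivity "to detect differences in pre- and post-cleaning facial cleanliness, across different face cleaning practices". The ancillary objectives listed under Secondary outcomes put it as the ability of the two kinds of metric "to predict recent personal cleaning practices, across the three methods".

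The Procedure section schedules the measurements as follows.

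- Step 7, before washing: "Photograph and record current facial cleanliness, per qualitative cleanliness metrics (presence of ocular and nasal discharge, and flies".
- Step 8, before washing: "Wipe the skin of the child's forehead using a moist, sterile gauze pad", then score the gauze on the 11-point scale.
- Step 10: the allocated cleaning method.
- Step 11: "Wait 5 minutes for child's hands and face (and the caregivers' hands) to air dry if Protocols A or B have been followed", then "photograph the face and record whether the wash removed existing ocular and nasal discharge".
- Step 12: repeat the Ct swabs of the child's face and hands and the caregiver's hands.
- Step 15: "Swab child's face and hands of children and carers 1, 2, 4, 6 and 8 hours after face washing". Facial cleanliness at each of these visits is defined as discharge and flies.
- Step 16: the wipe instruction of step 8, repeated word for word, with no clock time.
- Step 17: a closing wash with soap, after which no measurement of the face is listed.

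**The concern.** Both statements of the aim need a reading of the new metric soon after the face has been cleaned. Under Intervention allocation all three groups clean the face, so there is no unwashed arm. The contrast between an uncleaned and a just-cleaned face exists only within a child, before versus after. If the wipe is not taken straight after cleaning, the trial has no just-cleaned reading of the new metric in any arm.

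The comparison with discharge is what suffers. Discharge is recorded straight after the wash; the wipe, as the steps are listed, is next taken at the end of follow-up. If the new metric then performed poorly, nobody could tell whether it is insensitive to cleaning or whether the skin had become dirty again. An analysis plan cannot repair this, because the reading will not have been taken.

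**Working it through.** No arithmetic beyond counting applies, and the plan gives no figure to reproduce. The check sets the two schedules side by side. Because step 16 has no clock time, the wipe is shown under two readings: (a) the steps in their listed order, and (b) step 16 taken as part of every step 15 visit.

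| Time | Discharge | Wipe, reading (a) | Wipe, reading (b) |
|---|---|---|---|
| Before washing | step 7 | step 8 | step 8 |
| Straight after washing | step 11 | none | none |
| 1 h | step 15 | none | step 16 |
| 2 h | step 15 | none | step 16 |
| 4 h | step 15 | none | step 16 |
| 6 h | step 15 | none | step 16 |
| 8 h | step 15 | step 16, by its position | step 16 |
| Time points | 1 + 1 + 5 = 7 | 1 + 1 = 2 | 1 + 5 = 6 |

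Reading (a) is the more natural one. Step 16 is a separate numbered step between the 1 to 8 hour visits and the closing wash, and step 15 lists what is recorded at each visit without naming the wipe. The row straight after washing is empty for the wipe under both readings.

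What each contrast contains can be written out. For a reading taken at time t after washing, the change from baseline is

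D(t) = C + R(t) + W(t),

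where C is the effect of the allocated cleaning, R(t) is re-soiling up to time t, and W(t) is the effect of any further washing. W(t) need not be zero: step 13 asks that the face not be washed again, but excepts a child who is particularly uncomfortable.

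- Discharge, step 11: t is close to zero, R and W are negligible, so D is close to C.
- Wipe, reading (a): only D(about 8 h) is observed, one quantity with three components. C cannot be separated out.
- Wipe, reading (b): the earliest is D(1 h), which still contains an hour of R and W.

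Readings that both metrics share under (a) are baseline and about 8 hours. A matched comparison at those two times is possible, but it estimates sensitivity to residual cleanliness at the end of the day, not to the change from before to after cleaning.

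The background section on facial hygiene interventions suggests that timing matters. In the cited randomised trial of 424 children, ocular discharge predicted washing in 63% at two hours, "reducing to only 54% in four hours from washing". That shows a cleanliness sign can fade within hours. It does not give the rate for forehead dirt.

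**The case against.** The strongest reply is that the comparison survives. Discharge is also scored at 8 hours, so the two metrics can be set against each other at matched times, and nothing in Statistical Analysis tells the analyst to pair step 11 discharge with a step 16 wipe. This stands. A reader might infer that the metrics cannot be fairly compared at all, or that any inferiority of the wipe would be purely an effect of timing. The protocol does not support that. It supports only the narrower statement that the immediate change on the new metric is not captured.

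Second, step 16 has no clock time and may have been meant for each visit. The data collection form and the trial design figure are not available to settle it. This also stands as a limit on the 8-hour timing. It does not fill the gap straight after washing, and staff following the numbered list would take no wipe there.

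Third, a reader might go from 63% and 54% to the conclusion that discrimination at 8 hours would be close to nil for all 470 children. That does not follow. The figures are for ocular discharge, not forehead colour; they come from a washed-versus-unwashed comparison that this trial does not contain; they stop at 4 hours; and the protocol does not explain how prediction was defined, so a chance level cannot be read off. The protocol introduces the new metric because discharge tracks washing poorly, so one metric's decay cannot be assumed for the other.

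Finally, the aim is ancillary. That is correct and limits the importance of the point, but the aim is stated explicitly and the schedule for meeting it belongs in the protocol.

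**Conclusion.** The point holds in this form. The Procedure schedules no forehead wipe at the immediate post-wash assessment: zero readings there for the new metric against one for discharge, under either reading of step 16. As listed, the wipe has two time points to discharge's seven, and its before-after contrast combines cleaning, hours of re-soiling and any extra washing. The stated aim can then be addressed only as residual cleanliness at about 8 hours, through a matched comparison with 8-hour discharge.

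The figure of about 8 hours assumes that step 16 falls where it is listed; if it is repeated at each visit, the first post-wash wipe is at 1 hour. The conclusion also assumes that no form outside the text adds a wipe. The size of the loss in sensitivity cannot be derived, because the protocol gives no re-soiling rate for the forehead. The primary Ct outcome is not affected. The schedule should be changed before fieldwork, since a missing reading cannot be recovered later.

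**What to change.** Schedule a post-wash forehead wipe in all three arms directly after the step 12 swab, and make the head-to-head comparison with the step 11 discharge record. Two details matter.

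- Order: step 10 says the face should touch nothing until the next swab, so the wipe must follow that swab and not accompany the step 11 photograph. The forehead is not among the face-swab sites listed in step 9.
- Site: the step 8 wipe itself cleans the skin. The second wipe should use a standardised adjacent area of forehead not wiped at step 8; otherwise it would look cleaner whichever method was allocated.

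Record the time from cleaning to the wipe, because the 5-minute wait is stated only for Protocols A and B. Give step 16 a clock time and, if it is kept, label it an end-of-follow-up reading to be compared with discharge at the same visit.

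If an immediate wipe is not wanted, restate the aim as cleanliness about 8 hours after washing.

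The cost is one gauze and a few minutes per child, with one more photograph and score to process. No new equipment is needed and the sample size does not change.
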